1.0 INTRODUCTION

Title	Functional Liver Imaging with Sulfur Colloid SPECT/CT in Primary and Metastatic Liver Cancer Patients Receiving Liver-Directed Treatment: A Pilot Study
Short Title	Sulfur Colloid SPECT/CT for Liver Cancers
Phase	Pilot Study
Methodology	Single Arm Open-Label
Study Duration	4 years
Study Center(s)	University of Washington Medical Center
Objectives	Study the use of SPECT/CT imaging with ^{99m} Tc sulfur colloid to characterize functional liver in patients receiving liver-directed treatments for liver cancers, and characterize liver tissue response to these treatments. The long-term goal is to use functional liver imaging to personalize liver-directed therapies in liver cancer patients by improving risk stratification and reduce treatment-related hepatotoxicity.
Number of Subjects	60 evaluable subjects
Diagnosis and Main Inclusion Criteria	Patients diagnosed with primary (hepatocellular carcinoma, cholangiocarcinoma) and metastatic liver cancers receiving liver-directed therapies (external beam radiation therapy, surgery).
Study Product, Dose, Route, Regimen	99mTc sulfur colloid SPECT/CT scans
Duration of administration	Drug administration will consist of 3 SPECT/CT scans with ^{99m} Tc sulfur colloid (one baseline scan which is standard of care, two follow-up scans which are experimental and paid for by departmental research funds).
Statistical Methodology	^{99m} Tc sulfur colloid SPECT/CT parameters will be extracted, selected, and tested for statistical association to clinical liver function status and post-treatment toxicity using a variety of statistical methodologies. Receiver-operator characteristic (ROC) analysis will determine the optimal operating point for liver function classification accuracy using SC SPECT/CT parameters. Hypothesis testing of differences between independent groups will proceed using non-parametric Wilcoxon ranksum between 2 groups or Kruskal-Wallis ANOVA between >2 groups. Hypothesis testing of differences between imaging time points of the same subjects will proceed using non-parametric Wilcoxon sign-rank or Friedman ANOVA paired comparison. Survival analysis will consist of Kaplan-Meier estimation, log rank testing, and Cox proportional hazard regression. Dose-response models will be constructed from linear and logistic regression. Prediction models will utilize robust feature selection and feature fitting through multi-fold cross validation as part of a general machine learning framework.

This document is a protocol for a human research study. This study is to be conducted according to US and international regulations, applicable government regulations and Institutional research policies and procedures.

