4.0 STUDY DESIGN

General Design

This is a pilot study of utilizing SPECT/CT imaging with 99m Tc-SC to accurately identify and quantitate functional liver tissue on serial imaging in patients receiving RT or surgery for liver cancer. The long-term goals are to use functional imaging to improve risk stratification for selecting which patients should undergo aggressive local treatments with RT or surgery and to aid in RT planning by preferentially sparing functional liver tissue, thereby leading to reduced liver toxicity. There will be two cohorts of patients: those receiving RT (Cohort A) and those undergoing surgery (Cohort B). A total of 60 patients will be enrolled (Cohort A, n = 40; Cohort B, n = 20).

All patients will have a total of 3 SPECT/CT imaging with ^{99m}Tc-SC. The first scan in both cohorts will be routine medical care (not experimental) and will take place prior to initiation of RT or surgery. Two follow up scans will be part of the protocol. In cohort A, the first follow up scan will occur at mid-RT, and the second one about 1 month post-RT (prior to any potential anatomical liver changes). In cohort B, the first follow-up scan will occur 3-5 days postoperatively (prior to any potential liver hypertrophy), and the second one about 1 month post-operatively (when liver hypertrophy is expected to occur).

Endpoints

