radiation treatment planning scan, and will be used to identify functional liver tissue both miside and outside the radiation fields. Two follow-up scans will be used to determine the effects of RT and surgery on liver function. In the radiation therapy cohort, the first follow-up scan will be obtained midtreatment and the second will be obtained 1 month post-treatment. Detailed radiation dose response curves will be generated from these data. In the surgery cohort, the first follow-up scan will be obtained 3-5 days post-surgery and the second will be obtained 1 month post-surgery +/- 2 to 6 weeks post-surgery.

For the surgery cohort, an additional IV contrast enhanced CT scan (70 second delay) will be obtained immediately following the SPECT/CT scan for all 3 SPECT/CT scans. Since the anatomic FLR will be delineated and calculated using portal and hepatic veins as landmarks for segmental division, these IV contrast CT scans will be important in identifying these blood vessels accurately.

Criteria for Removal/Withdrawal from Treatment

Patients will be withdrawn from treatment if their clinical conditions decline to the point that they are no longer able to tolerate SPECT/CT with ^{99m}Tc sulfur colloid. They will be withdrawn from treatment if they are enrolled into hospice.

Patients will still receive follow-up care per standard of care even if they withdraw from the study. If a subject withdraws consent to participate in the study or aspects of the study, attempts will be made to obtain permission to record at least survival data up to 6 months post-treatment.

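### The synopsis counts 60 evaluable subjects and the design enrols 60 in total, so 60 evaluable is not assured for the paired and change analyses

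*Combined protocol and SAP*

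**What the plan says.** The synopsis in section 1.0, under Number of Subjects, reads "60 evaluable subjects". The General Design text in section 4.0 reads "A total of 60 patients will be enrolled (Cohort A, n = 40; Cohort B, n = 20" (closing bracket omitted here). The same section sets the data expected from each patient: "All patients will have a total of 3 SPECT/CT imaging", meaning one before treatment and two afterwards.

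Section 7.0, Criteria for Removal/Withdrawal from Treatment, provides three routes out:

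- Clinical decline: "Patients will be withdrawn from treatment if their clinical conditions decline to the point that they are no longer able to tolerate" the study scan.
- Hospice: "They will be withdrawn from treatment if they are enrolled into hospice".
- Withdrawn consent: the text beginning "If a subject withdraws consent to participate in the study or aspects of the study" says only that permission will be sought to record at least survival up to 6 months after treatment. That does not supply scans.

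The protocol contains no definition of *evaluable*, no expected loss rate, no replacement rule and no justification of the sample size.

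**The concern.** The same number is used for two different quantities. If 60 is the number analysed, more than 60 must be enrolled or lost patients must be replaced. If 60 is the number enrolled, fewer will be analysed wherever a follow-up scan is needed.

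The analyses at stake are those that compare scans over time. Primary objective (b) relates post-treatment change in uptake to change in clinical liver function. Secondary objectives (a) and (b) model uptake change against radiation dose. Secondary objective (c) relates remnant uptake to hypertrophy after resection. The synopsis plans signed-rank and Friedman comparisons for these repeated scans, and a standard Friedman test uses only patients with every time point being compared. A reader who takes the synopsis at its word will expect more precision than the design is set up to give.

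Cohort B is the more exposed, because one patient lost out of 20 is 5% of that cohort. The decline and hospice routes would also tend to remove the sickest patients, who carry much of the information on toxicity and loss of liver function.

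**Working it through.** **1. Reproduce the plan's figure.** Cohort A 40 + cohort B 20 = 60 (section 4.0). The sum is correct. It is a count of patients enrolled and equals the synopsis figure exactly, so the margin for loss is 60 − 60 = 0. The documents give no significance level, power, effect size or dropout rate, so 60 cannot be derived in any other way.

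**2. Condition for both statements to hold.** With a loss proportion d, expected evaluable patients = 60 × (1 − d). This equals 60 only when d = 0.

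**3. Size under assumed loss.** The documents give no d, so the values below are assumptions. Here d is the overall proportion of enrolled patients who do not supply the scans a given analysis needs. Interval width is taken as proportional to 1/√n, so the widening relative to 60 is √(60/n).

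| Assumed loss d | Evaluable, 60 × (1 − d) | Cohort A, 40 × (1 − d) | Cohort B, 20 × (1 − d) | √(60/n) |
|---|---|---|---|---|
| 0% | 60 | 40 | 20 | 1.00 |
| 5% | 57 | 38 | 19 | 1.03 |
| 10% | 54 | 36 | 18 | 1.05 |
| 20% | 48 | 32 | 16 | 1.12 |

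**4. How likely is no loss at all?** If patients are lost independently of one another with probability d, P(all 60 remain) = (1 − d)^60. This is 0.98^60 = 0.30 at 2%, 0.95^60 = 0.046 at 5%, and 0.90^60 = 0.002 at 10%. Even a low loss rate makes a full set of 60 unlikely.

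**5. Which analyses are affected?**

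- Primary objective (a) relates the pre-treatment scan to liver function, survival and post-hepatectomy liver failure. Sections 4.0 and 7.0 describe that scan as standard care taken before treatment, so a patient who later declines or enters hospice has already supplied it. Loss here is confined to patients who consent but are never scanned, or whose outcome is not obtained.
- Primary objective (b) and the secondary objectives need a follow-up assessment as well as the baseline. The table applies to these.

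**The case against.** The strongest reply has four parts.

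First, there is no arithmetic error. The cohorts add up, and the study is a labelled pilot whose sample size supports no stated power or precision. That stands, and the point here concerns two inconsistent statements of size, not a failed calculation.

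Second, *evaluable* is undefined. If it means only that the baseline scan was obtained, 60 enrolled may give close to 60 evaluable. This also stands, and it is why the shortfall can be called only not assured, and only for the change analyses. It does not remove the problem, because a primary objective and all the secondary objectives look beyond the baseline scan.

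Third, the protocol limits loss. Exclusion 5.1.8 removes patients who do not plan to keep to follow-up. The second scan falls during radiation or, in cohort B, during the inpatient stay. The third scan has a generous window in section 7.0. These features argue for the lower end of any assumed range, but they do not bring loss to zero.

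Fourth, the synopsis might mean that accrual continues until 60 patients are evaluable. Section 4.0 caps enrolment at 60 and no replacement rule exists, so the current text does not support that reading.

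Two stronger inferences are tempting and should be resisted. A reader might conclude that the study will miss its sample size or be underpowered. The documents give neither a loss rate nor a power target, so neither follows. A reader might also assume 10% to 20% loss at each follow-up scan and conclude that complete three-scan sets number only 60 × 0.9 × 0.9 = 48.6 to 60 × 0.8 × 0.8 = 38.4. That requires the two scans to be missed independently. Decline, hospice and withdrawal tend to remove later scans together, and if the same patients miss both, complete sets number 54 to 48. Even under independence, patients with a baseline and at least one follow-up scan would number 60 × (1 − 0.01) = 59.4 to 60 × (1 − 0.04) = 57.6. The 49-to-38 range should not be used unless independence is stated as an assumption.

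**Conclusion.** The two statements of sample size agree only with zero loss, and the protocol itself provides for loss. As written, 60 evaluable is not assured for the paired and change analyses, while the baseline analyses of objective (a) are little affected. The shortfall cannot be taken from the documents. Under an assumed overall loss of 5% to 20% it is 3 to 12 patients (2 to 8 in cohort A, 1 to 4 in cohort B), with intervals about 3% to 12% wider than at 60.

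The inconsistency itself does not depend on those assumed rates, since any loss above zero produces it. The consequence is modest: somewhat less precision than the synopsis implies, in a pilot study with no stated power. It is worth correcting because 60 is the only sample-size information a reader has.

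**What to change.** Restate Number of Subjects in the synopsis as 60 enrolled (40 in cohort A, 20 in cohort B), matching section 4.0. Then define and state the evaluable number separately, by cohort:

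- **Baseline analyses:** patients with the baseline scan obtained.
- **Change analyses:** patients with the baseline scan and the follow-up scan being analysed.

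Show the loss rate assumed for each. The sponsor should choose that rate from its own experience; the 5%, 10% and 20% used here are illustrations and not proposed values.

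This changes wording only. The downside is that the stated figure becomes slightly less favourable.

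If the sponsor does mean 60 evaluable for the change analyses, the alternative is a replacement rule or a larger enrolment. Using n/(1 − d) rounded up within each cohort, enrolment would be 43 + 22 = 65 at 5% loss, 45 + 23 = 68 at 10%, and 50 + 25 = 75 at 20%. That route costs more, because each added patient brings up to two research scans, which the synopsis says are paid for from departmental research funds.

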2.0 BACKGROUND

Study Disease

Hepatocellular carcinoma (HCC) is the most common primary liver cancer in the world and is one of the most rapidly growing causes of cancer-related death in the United States [1]. Multiple liver-directed treatment options are available to HCC patients, including liver transplantation, surgical resection,

radiofrequency ablation, catheter-based therapies, and radiation therapy (RT). HCC tumors often arise in the background of chronic liver disease such as alcohol, viral hepatitis, autoimmune hepatitis, or non-alcoholic fatty liver disease-related cirrhosis. Patients with cirrhosis commonly have impaired liver function, which plays a central role in determining which treatments patients can safely receive and how aggressive these treatments can be. Ultimately, tumor eradication with preservation of liver function is the desired treatment goal for HCC patients.

Technological advances in the field of radiation oncology have now made it possible to deliver high ablative or near-ablative doses of focal partial liver radiation with excellent local control rates of 70-90% after stereotactic body radiation therapy or proton beam therapy [2-4]. Similarly, advances in surgical techniques along with proper patient selection has allowed for encouraging 5-year overall survival rates of 50-70% despite more extensive resections [5]. Liver failure is the most serious and major cause of morbidity and mortality after treatment in HCC patients and arises primarily as a result of inadequate functional liver reserve post-treatment. Despite the most sophisticated radiation techniques, radiationinduced liver disease (RILD) can still develop in 5-67% of patients, depending on the baseline liver function and volume of liver irradiated, with fatal RILD in up to 5-7% [6-9]. Post-hepatectomy liver failure (PHLF) in resected HCC patients can occur in 5-20% of patients and is primarily dependent on the extent of resection and degree of pre-surgical liver dysfunction [10-12]. Potential reasons for the difficulties in mitigating these RILD and PHLF rates are the reliance on conventional assessments of liver function and on anatomical information of liver function to predict post-treatment liver toxicities. Furthermore, there are a group of patients that may not be offered potentially curative partial liver radiation or partial hepatectomy due to the fear of RILD or PHLF based on these crude conventional measurements of liver function and reserve post-treatment.

Currently, evaluation of global liver function routinely incorporates conventional laboratory blood tests (e.g. bilirubin, albumin, coagulation factors) and clinical variables (e.g. presence of ascites or hepatic encephalopathy) that indirectly measure liver function. They form the basis of clinical scoring systems such as the Child-Turcotte-Pugh (CTP) system that characterize liver dysfunction. However, these assessment tools are susceptible to subjectivity (clinical assessment of degree or severity of ascites and hepatic encephalopathy) and confounding factors (malnutrition affecting albumin) and may be unreliable in predicting hepatotoxicity after liver-directed treatment [13]. Small changes in the component lab values, for example, can lead to more significant score changes that may not truly reflect liver dysfunction, and transition between CTP classes can have major impact on patient management.

Perhaps more importantly, current models estimating the risk of liver toxicity are based upon estimating the threshold volume of non-tumor liver receiving a certain dose of radiation (RILD prediction) or the estimated volume of liver remaining after surgical resection (PHLF prediction) that is defined and delineated on computed tomography (CT) imaging. CT volumetry, however, is based solely on anatomic characteristics and provides no information on the spatial functional capacity or heterogeneity of the liver parenchyma. Furthermore, many patients planned to undergo RT or surgery have already received prior liver-directed or systemic therapies. It is known that the number of prior liver-directed therapies is a major contributor to worsening of liver function after RT [14], and preoperative chemotherapy can cause liver injury that results in increased morbidity and mortality after surgery [15]. It may be possible that the wide ranges in reported RILD and PHLF are due in part to the unaccounted effects of prior liver-directed and systemic therapies on liver function where regions of compromised liver function are considered "normal" when they are in fact dysfunctional. Thus, an unmet need for the treatment of HCC patients is the ability to accurately depict global and regional liver function in order to better risk stratify patients a priori and personalize treatments by preferentially avoiding regions of highly functioning liver. This unmet need also exists for certain patients with metastatic cancer to the liver. Many patients with colorectal cancer metastatic to the liver planned to receive surgical resection of their liver disease, for example, have received significant amount of systemic chemotherapy prior to surgery that results in steatohepatitis. Studies have shown that these patients are at high risk for perioperative morbidity and mortality [15]. Being able to more accurately assess the function of the future liver remnant noninvasively, therefore, would also be valuable.

Rationale for Use of SPECT/CT 99mTc-Sulfur Colloid Scans

^{99m}Tc sulfur colloid single-photon emission computerized tomography (SC SPECT/CT) imaging is a well-established FDA-approved diagnostic imaging modality for the evaluation of hepatic function, introduced by Harper et al. in 1965 [16]. Colloidal particles such as SC are primarily taken up and cleared by the reticuloendothelial (Kupffer) cells that line the sinusoids of the liver and serve as supporting cells to hepatocytes, as well as the spleen and bone marrow. It has been established that a close correlation exists between the function of hepatocytes and Kupffer cells. Hepatocytes and Kupffer cells also exhibit similar perfusion characteristics, are equally affected by liver fibrosis, and are proportionately distributed within the liver [17, 18]. Furthermore, multiple studies have demonstrated that SC distribution within the liver correlates well with histology in explanted livers [19], presence and severity of cirrhosis [20], and long-term clinical outcomes of hepatic failure-related mortality [21]. SC function, therefore, can be used as a surrogate for hepatic function.

While SC SPECT/CT is well-suited for the proposed aims, there are other imaging options. HIDA (99mTc-acetanilide iminodiacetic acid) or mebrofenin SPECT is directly related to hepatocyte function [22], but HIDA is preferentially extracted to the bile ducts, producing distinct uptake patterns which would confound the proposed heterogeneity analysis. Additionally, HIDA protocols use dynamic SPECT, which presents challenges such as increased imaging time and analysis workload, uncertain impact of detector geometric dependence over the dynamic imaging course, and general limitations of image-based input functions for SPECT [23]. MRI tracers are of interest including Gd-EOB-DTPA, a hepatocyte-specific contrast agent [24, 25], as well non-specific Gd contrast, the perfusion of which may correlate to ICG clearance [26]. While promising, MRI is more problematic for radiomics and correlation with radiation dose maps due to the possibility of geometric distortion, susceptibility artifacts from implanted fiducial markers, and issues with quantitative accuracy and uniformity inherent to MRI.

Clinical Data to Date

Detection of livery injury by radiation was first demonstrated in the late 1960's using 2-dimensional planar scintigraphy [27-29]. The inability to obtain 3-dimenstional spatial assessment of SC distribution in the liver and spleen hampered the routine use of SC in the clinic as well as application into the radiation and surgical oncology fields. Recently, the development of SPECT/CT technology has allowed improved regional contrast resolution relative to planar scintigraphy between functional, dysfunctional and non-functional liver from tomographic image acquisition, along with increased accuracy in local SC activity estimation from CT-based attenuation correction [30, 31]. Modern SC SPECT/CT imaging techniques, therefore, provide the potential for volumetric and spatial characterization of liver function prior to and in response to therapy. Preliminary retrospective data from our group have shown that measuring "total liver function" (derived from the product of functional liver volume and liver-to-spleen mean uptake) on pre-treatment SC SPECT/CT in 30 HCC patients may improve risk stratification and outcome prediction [32]. These data need to be validated prospectively with standardization of imaging protocols. Furthermore, changes in global or regional liver function as assessed with SC SPECT/CT, however, have not been studied in the context of RT and surgical resection of the liver.

Risks/Benefits

The primary risk to patients in this study is the risk associated with the two additional SPECT/CT ^{99m}Tc-SC scans. The radiation treatments or surgery that patients receive will be standard of care. Risks associated with the two SPECT/CT ^{99m}Tc-SC scans include: patient time (approximately 1 hour per scan); radiation dose from radioactive tracers and CT scans (up to ~ 30 mSv per session, which is about 0.1% of the usual radiation dose for liver cancer treatment, typically around 60 Gy), and intravenous injection and associated potential for bleeding, pain, infection, and injection site reaction.

In patients who opt to undergo the indocyanine green clearance study, there is the risk of art additional intravenous access procedure for the injection of the indocyanine green dye (injection of the indocyanine green must be separate from the intravenous access of the blood draw). Please see consent form for further details on potential risks.

The benefit gained from this study is the knowledge of whether SPECT/CT ^{99m}Tc-SC scans can identify, visualize, and quantify functional liver tissue. In doing so, we can preferentially protect those liver regions from radiation to decrease radiation induced liver injury in patients treated with radiation therapy. In surgical patients, we can potentially predict the risk of liver decompensation and perioperative morbidity more accurately prior to surgery by more accurately quantifying the function of the future liver remnant. We will also learn about the effect of radiation and surgery on the spatial and temporal dynamics of liver function and recovery, which can help us improve and potentially expand our patient selection for aggressive liver-directed therapies and design individualized treatments to safely treat liver tumors while minimizing liver toxicity.

